6.1.1 Devices

No devices for administration of study drug will be used in this study.

6.2 PREPARATION/HANDLING/STORAGE/ACCOUNTABILITY

6.2.1 Storage and handling

1. The Investigator or designee must confirm appropriate temperature conditions have been maintained during transit for all study intervention received and any discrepancies are reported and resolved before use of the study intervention.
2. Only participants enrolled in the study may receive study intervention and only authorized site staff may supply or administer study intervention. At site, all study intervention must be stored in a secure, environmentally controlled, and monitored (manual or automated) area in accordance with the labeled storage conditions with access limited to the Investigator and authorized site staff.
3. During transportation from the study site to the participant's home and at the participant's home, study intervention must be handled/stored as per instructions of the Study Drug Transportation Guidelines and the Patient User Instruction Manual. Participant/parent/legally authorized representative/caregiver should be trained by the site staff to ensure that IMP is handled and stored properly at participant's home.
4. The Investigator, institution, or the head of the medical institution (where applicable) is responsible for study intervention accountability, reconciliation, and record maintenance (ie, receipt, reconciliation, and final disposition records).

6.2.2 Responsibilities

Any quality issue noticed with the receipt or use of an IMP (deficiency in condition, appearance, pertaining documentation, labeling, expiration date, etc) must be promptly notified to the Sponsor. Some deficiencies may be recorded through a complaint procedure (see [Section 8.5.9](#)).

A potential defect in the quality of IMP may be subject to initiation of a recall procedure by the Sponsor. In this case, the Investigator will be responsible for promptly addressing any request made by the Sponsor, in order to recall the IMP and eliminate potential hazards.

Under no circumstances will the Investigator supply IMP to a third party (except for Direct-to-Patient (DTP) shipment, for which a courier company has been approved by the Sponsor), allow the IMP to be used other than as directed by this clinical trial protocol, or dispose of IMP in any other manner.

6.3 MEASURES TO MINIMIZE BIAS: RANDOMIZATION AND BLINDING

The study is open-label study without a treatment control or placebo group in patients. To control bias, the following measures are taken:

- Healthy participants will serve as a reference comparator group for interpreting study results.
- PROs will be collected by electronic data capture.
- Efficacy data will be measured by the same device model.
- Biomarker data will be measured by an experienced laboratory.
- Study is limited to 2 to 4 very experienced study centers.
- Standardized study assessment procedures.
- Standardized photography for targeted lesional areas, and clinical disease severity and PRO evaluations.
- Reason for screen failures (if any) will be documented.

6.4 STUDY INTERVENTION COMPLIANCE

Investigator or his/her delegate must ensure that IMP will be administered to each participant according to the labeling instructions.

IMP accountability:

- Intervention units are returned by the participant at the next study visit. In case of DTP emergency process, the intervention units can be returned by the carrier (if defined in the contract).
- The Investigator counts the number of remaining unused kits/pre-filled syringes, and fills in the IMP accountability and inventory forms.
- The Investigator or his/her delegate records the dosing information on the appropriate page(s) of the eCRF.
- The monitor in charge of the study then checks the eCRF data by comparing them with the IMP which he/she has retrieved and source documents.

When participants are dosed at the site (see [Section 1.3](#)), they will receive study intervention directly from the Investigator or designee, under medical supervision. The date and time of each dose administered in the clinic will be recorded in the source documents and recorded in the eCRF. The dose of study intervention and study participant identification will be confirmed at the time of dosing by a member of the study site staff other than the person administering the study intervention.

When participants self-administer study intervention(s) at home (see [Section 1.3](#)), they will document compliance on a home dosing diary. Compliance with study intervention will be assessed at each visit. Deviation(s) from the prescribed dosage regimen should be recorded in the eCRF.

6.5 CONCOMITANT THERAPY

Any allowed medication or vaccine (including over-the-counter or prescription medicines, vitamins, and/or herbal supplements, [live vaccine is prohibited]) that the participant is receiving at the time of enrolment or receives during the study must be recorded in the eCRF along with:

- Reason for use.
- Dates of administration including start and end dates.
- Dosage information including dose and frequency.

Any change in concomitant medication must be recorded.

Participants must abstain from taking prohibited prescription drugs within 4 weeks before the Screening Visit or 5 half-lives (whichever is longer) until the Week 21 (EoS Visit), unless, in the opinion of the Investigator and Sponsor, the medication will not interfere with the study.

Paracetamol/acetaminophen, at doses of ≤ 2 g/day, is permitted for use any time during the study, except for 12 hours prior to a visit or clinical assessment to prevent any bias to itch related PRO assessments. Other concomitant medication may be considered on a case-by-case basis by the Investigator in consultation with the Sponsor representative(s), if required.

6.5.1 Rescue medicine

During Treatment Period, if medically necessary (ie, to control intolerable AD symptoms on face and genital areas), rescue treatment for AD may be provided to participants at the discretion of the Investigator (ie, topical treatment with high potency topical corticosteroids [TCS]). Investigators should make every attempt to conduct efficacy and safety assessments (eg, disease severity scores, safety laboratory assessments) immediately before administering any rescue treatment. An unscheduled visit may be used for this, if necessary.

Investigators will be required to perform an IGA evaluation prior to starting rescue treatment and initiate rescue treatment only in patients who either have an IGA score of 4, or have intolerable AD symptoms. The date and time of rescue medication administration as well as the name and dosage regimen of the rescue medication must be recorded in the eCRF.

6.5.2 Prohibited medications and procedures

Treatment with the following concomitant medications and procedures is prohibited within 4 weeks before the Screening Visit or 5 half-lives (whichever is longer) until the Week 21 (EoS Visit):

1. Topical treatment used for the treatment of AD or for super-infection:
 - Topical calcineurin inhibitors (tacrolimus or pimecrolimus).
 - Topical phosphodiesterase inhibitors (crisaborole).
 - Topical corticosteroids.

2. Topical antibiotics.
3. Topical immunosuppressive/immunomodulating treatment.
4. Monoclonal antibodies (mAbs) within 5 half-lives or within 6 months before the Screening Visit if the half-life is unknown.
5. Antihistaminic medication, H2 receptor antagonists.
6. Systemic treatment for AD with an immunosuppressive/immunomodulating agent (including, but not limited to, systemic corticosteroids, cyclosporine A [CsA], azathioprine [AZA], methotrexate [MTX], mycophenolate mofetil [MMF], Interferon gamma [IFN- γ], or other biologics).
7. Biologic therapy/systemic immunosuppressant to treat inflammatory disease or autoimmune disease (eg, rheumatoid arthritis, inflammatory bowel disease, primary biliary cirrhosis, systemic lupus erythematosus, multiple sclerosis, etc).
8. Treatment with immune modulating biologics including, but not limited to, the following:
 - Any cell-depleting agents (eg, rituximab).
 - Infliximab, adalimumab, golimumab, certolizumab pegol, abatacept, etanercept, or anakinra.
9. Leukotriene antagonists/modifiers within, unless patient is on a continuous treatment for at least 4 weeks before the Screening Visit.
10. Antifibrinolytic tranexamic acid or epsilon-aminocaproic acid.
11. Intravenous immunoglobulin (IVIG) therapy and/or plasmapheresis.
12. Procedures used for the treatment of AD:
 - Phototherapy (such as ultraviolet B [UVB], narrowband UVB [NBUVB], ultraviolet A1 [UVA1], or psoralen-UVA [PUVA]).
 - Bleach baths.
 - Use of a tanning booth/parlor.

For patients having participated recently in a clinical study with an investigational new drug which is not approved in the specific country concerned and for which the PK or pharmacodynamic half-life is not known, the wash out period between last intake of investigational new drug and screening visit should be ≥ 6 months.

In addition, participants will be asked to abstain from live (attenuated) vaccinations through Week 21. If a participant requires a vaccination prior to 12-weeks after discontinuing treatment with dupilumab, titers should be checked post-vaccination. Live (attenuated) vaccinations include but are not limited to the following:

- Bacillus Calmette-Guérin (BCG).
- Chickenpox (Varicella).
- FluMist-Influenza.

- Intranasal influenza.
- Measles (Rubeola).
- Measles-mumps-rubella (MMR) combination.
- Measles-mumps-rubella-varicella (MMRV) combination.
- Mumps.
- Oral polio (Sabin).
- Oral typhoid.
- Rotavirus.
- Rubella.
- Smallpox (Vaccinia).
- Varicella Zoster (shingles).
- Yellow fever.

NOTE: For participants who have vaccination with live attenuated vaccines planned during the course of the study (based on national vaccination schedule/local guidelines), it will be determined, after consultation with a physician, whether the administration of vaccine can be postponed until after the EoS, or preponed to before the start of the study without compromising the health of the participant:

- Patient for whom administration of live (attenuated) vaccine can be safely postponed would be eligible to enroll into the study.
- Patients who have their vaccination preponed can enroll in the study only after a gap of 4 weeks following administration of the vaccine.

6.5.3 Permitted medications

Other than the prohibited medications and procedures listed in [Section 6.5.2](#), treatment with concomitant medications and procedures is permitted during the study. This includes nasal and inhaled corticosteroids. The use of these medications should be recorded.

6.6 DOSE MODIFICATION

No change in IMP dose is allowed. Patients who discontinue treatment with IMP will be excluded from further participation.

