- b Participants who discontinue the study treatment prematurely the end of treatment (EoT) assessments will be performed at the time of discontinuation to assure a complete clinical assessment in close temporal proximity to the premature termination of study treatment. In addition, to allow assessment of participant outcomes over the stipulated study period, participants will be asked and encouraged to complete all remaining study visits and participate in all assessments according to the visit schedule.
- c Electronic diary will be dispensed to the patients at Screening Visit (V1) and will be collected on Week 21 (Visit 6). The PROs will be administered to patients via eDiary. Patients will bring the eDiary to the site at each visit, and it will be reviewed and dispensed back to patients at each visit.
- d For future use and exploratory research; collection is optional; whole blood sample for DNA extraction will be collected at baseline only.
- e Biopsy (4 mm). Skin biopsy in AD participants will be collected in lesional tissue, with acute lesions. Excluding oozing, infections and chronic stages - lichenification. Preferably in the forearms followed by back.
- f Post-lesional healed or healing skin should localisation matched to the baseline pruritic lesional biopsy; if post-lesional healed skin that is completely non-pruritic non-lesional is not available at later visits, one of the following biopsies should be collected (in the order of relevance): 1. lesional non-pruritic skin, 2. Post-lesional pruritic skin or 3. lesional pruritic skin
- g Optional.
- h The IMP will be administered every 14 ± 2 days (Q2W) during the 16-week treatment period.
- i Self administration by AD patients or caregivers at home.
- j Whole blood sample collected at baseline and stored during the study for potential analysis if deemed necessary for safety reasons. Will be described in study reference manual.
- k Vital signs, including heart rate, systolic and diastolic blood pressure (mmHg), and body temperature (°C) will be measured.
- l Urine pregnancy test could be performed at home with or without the assistance of a home care provider. In case of positive urine test the study treatment will be withheld and a serum pregnancy test should be performed as soon as possible, to confirm the pregnancy. Pregnancy will lead to definitive treatment discontinuation in all cases.
- m Participants self assessment.

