7 DISCONTINUATION OF STUDY INTERVENTION AND PARTICIPANT DISCONTINUATION/WITHDRAWAL

7.1 DISCONTINUATION OF STUDY INTERVENTION

7.1.1 Definitive discontinuation

In rare instances, it may be necessary for a participant to permanently discontinue (definitive discontinuation) study intervention. If study intervention is definitively discontinued, the participant will be asked to remain in the study to be evaluated for clinical assessments (including PRO) and collection of a skin biopsy.

Pregnancy in a female participant will lead to definitive intervention discontinuation in all cases.

Handling of participants after definitive intervention discontinuation

Participants will be followed-up according to the study procedures specified in this protocol up to the scheduled date of study completion, or up to recovery or stabilization of any AE to be followed-up as specified in this protocol, whichever comes last.

If possible, and after the definitive discontinuation of intervention, the participants will be assessed using the procedure normally planned for the last dosing day with the IMP.

All cases of definitive intervention discontinuation must be recorded by the Investigator in the appropriate pages of the eCRF when considered as confirmed.

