7.2 PARTICIPANT DISCONTINUATION/WITHDRAWAL FROM THE STUDY

- A participant may withdraw from the study at any time at his/her own request, or may be withdrawn at any time at the discretion of the Investigator for safety, behavioral, compliance, or administrative reasons.
- At the time of discontinuing from the study, if possible, an early discontinuation visit should be conducted.
- The participant will be permanently discontinued both from the study intervention and from the study at that time.

- If the participant withdraws consent for disclosure of future information, the Sponsor may retain and continue to use any data collected before such a withdrawal of consent.
- If a participant withdraws from the study, he/she may request destruction of any samples taken and not tested, and the Investigator must document this in the site study records.

If participants no longer wish to take the IMP, they will be encouraged to remain in the study. The patients may withdraw from treatment with the IMP, if they decide to do so, at any time and irrespective of the reason, or this may be the Investigator's decision. All efforts should be made to document the reason(s) for treatment discontinuation and this should be documented in the eCRF.

The Investigators should discuss with them about the key visits to be attended. The value of all their study data collected during their continued involvement will be emphasized as important to the public health value of the study.

Participants who withdraw from the study intervention should be explicitly asked about the contribution of possible AEs to their decision, and any AE information elicited must be documented. Preferably the patient should withdraw consent in writing and, if the patient or the patient's representative refuses or is physically unavailable, the site should document and sign the reason for the patient's failure to withdraw consent in writing.

All study withdrawals should be recorded by the Investigator in the appropriate screens of the eCRF and in the participant's medical records. In the medical record, at least the date of the withdrawal and the reason should be documented.

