9.3 POPULATIONS FOR ANALYSES

The following populations are defined ([Table 3](#)):

Table 3 - Populations for analyses

| Population | Description |
|-----------------------|--|
| Enrolled | All participants who sign the ICF |
| Intent-to-treat (ITT) | All enrolled patients, who received at least 1 dose of IMP and all enrolled healthy participants who have at least 1 skin biopsy performed, irrespective of compliance with the study protocol and procedures. |

| Population | Description |
|---------------------|---|
| Modified ITT (mITT) | All ITT participants. If prohibited therapies for AD (see Section 6.5.3) are used and assessed by the study team as having a significant impact on skin biopsy assessment, only visits prior to rescue treatment use are considered. |
| Safety | The safety population includes all patients, who actually received at least 1 dose of IMP or had at least 1 skin biopsy and all healthy participants who had a skin biopsy or another safety assessment performed |

Abbreviations: AD: atopic dermatitis, ICF: informed consent form; IMP: investigational medicinal product; ITT=intent-to-treat, mITT: modified ITT.

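### Section 6.6 removes patients who stop IMP from the study, while Sections 7.1.1, 7.2 and SoA footnote b ask them to stay and complete the remaining visits

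*Protocol*

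**What the plan says.** Protocol Section 6.6 (Dose modification) rules out any change of dose and then says: "Patients who discontinue treatment with IMP will be excluded from further participation". It has no qualifier and no cross-reference.

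Three other places in the current protocol deal with the same patients:

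- Section 7.1.1, on definitive discontinuation: "the participant will be asked to remain in the study to be evaluated for clinical assessments (including PRO) and collection of a skin biopsy". It continues: "Participants will be followed-up according to the study procedures specified in this protocol up to the scheduled date of study completion", or until adverse events have recovered or stabilised if that is later.
- Section 7.2: "If participants no longer wish to take the IMP, they will be encouraged to remain in the study".
- Section 1.3, SoA footnote b: after premature discontinuation the EoT "assessments will be performed at the time of discontinuation to assure a complete clinical assessment in close temporal proximity to the premature termination" of treatment, and in addition "participants will be asked and encouraged to complete all remaining study visits and participate in all assessments according to the visit schedule".

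For people who leave the study altogether, Section 7.2 adds: "At the time of discontinuing from the study, if possible, an early discontinuation visit should be conducted".

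Sections 5, 7.2 and 9.2 say that drop-outs are not replaced. Protocol Section 9.4.6 does not impute missing efficacy data, apart from a possible exception for values removed because of rescue therapy. SAP Section 1.2.6 imputes nothing.

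**The concern.** A site cannot follow both 6.6 and the other three texts, and the protocol nowhere says in terms which prevails. Only 2 to 4 centers are planned (Section 6.3), so one site reading 6.6 literally could treat a noticeable share of the participants differently.

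A patient removed under 6.6 would not attend at calendar Week 17, when the mandatory biopsies for both primary endpoints are due. That patient would also miss the Week 21 visit and the Week 29 safety call. With no replacement and no imputation, the scheduled Week 17 value would simply be absent. The loss is selective: it can fall only on people who stopped treatment, so the Week 17 and Week 21 summaries would lean towards those who completed it. The later safety contacts would be missing in the same people.

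**Working it through.** The plan gives no figure on this point to reproduce. The core check is a comparison of texts, followed by a count from the SoA and a small precision calculation.

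**1. Do the texts really conflict?** Section 6.6 ends participation when IMP stops. Sections 7.1.1 and 7.2 and footnote b keep the patient in the study after IMP stops. One bullet in 7.2 says that a participant is permanently discontinued from both intervention and study, but it follows the sentence on leaving the study and so covers withdrawal, not stopping IMP alone. It does not reconcile 6.6 with the rest. All four texts are current, not amendment-log text.

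**2. What survives a 6.6 exit?** Footnote b is attached to Visit 5, the Week 17 (EoT) column, which includes the post-lesional biopsy. Its first part places that set at discontinuation and carries no condition of feasibility. A site can do it and then end participation, so this part is compatible with 6.6. The second part, the remaining visits, is not.

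**3. Scheduled contacts lost.** After Day 1 the SoA has five: site visits on D15, D43, D113 and D141, and the call on D197. For a premature discontinuer:

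| Last dose | Contacts still to come | Number |
|---|---|---|
| D1 | D15, D43, D113, D141, D197 | 5 |
| D15 or D29 | D43, D113, D141, D197 | 4 |
| D43, D57, D71 or D85 | D113, D141, D197 | 3 |

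D113 (Week 17), D141 (Week 21) and D197 (Week 29) are lost in every row. The EoT set at discontinuation is additional to this list.

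**4. Precision against plan.** Section 9.2 enrols about 34 with a 20% drop-out allowance: 34 × 0.20 = 6.8 lost, 34 × 0.80 = 27.2 left. The half-width of the 90% interval (protocol Table 4) for a mean change, in SD units, is t(0.95, n−1)/√n:

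- n = 34: 0.290
- n = 33 (1 lost): 0.295
- n = 28 (6 lost): 0.322
- n = 27 (the plan's own allowance): 1.706/√27 = 0.328

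The range of 1 to 6 lost is an assumption, because no stopping rate is given. Even 6 lost gives 0.322, inside the 0.328 already planned for.

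**5. Selective loss.** If k of 34 are missing, the mean of the rest differs from the mean of all 34 by (k/34) × (difference between the two groups). For k = 1 that is 1/34 = 0.029 of the difference; for k = 6 it is 6/34 = 0.176. The difference itself is unknown. The upper end would use nearly the whole 6.8 allowance on IMP discontinuers, so it should carry no weight as a forecast.

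**6. The pointer in 7.1.1.** A sentence there, prefaced by a condition of feasibility, refers to the procedures of the last dosing day. Section 6.1 puts that day at Week 15, and the SoA marks it as a home dose. The Week 17 column has 16 marked rows. Removing the site-visit marker, IMP accountability and the optional blood sample leaves 13. Five are also marked at Week 15: peak pruritus NRS, the block of other NRS scales, POEM, PROMIS-itch and DLQI. So 13 − 5 = 8 are absent: biopsy, vital signs, pregnancy test, photography, IGA, EASI, SCORAD and ADCT. Seven recur at Week 21 for those who stay; the Week 21 biopsy is optional.

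**The case against.** The best defence is that the protocol largely shows which rule governs. Section 8 makes adherence to the SoA a requirement of study conduct, and footnote b is part of the SoA. Section 7.1.1 is the dedicated section on discontinuation. Against these stands one sentence in a section on dosing, which might have been meant as exclusion from further dosing. This lowers the chance that a site acts on 6.6. It does not remove the contradiction, because the sentence speaks of participation.

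Three stronger readings are tempting, and the documents do not support them.

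- A reader might infer that 6.6 leaves discontinuers with no on-treatment or end-of-treatment biopsy. Footnote b places the EoT set at discontinuation unconditionally, so the loss is of the scheduled Week 17 sample, not of every post-baseline biopsy. The documents do not say whether an early EoT biopsy would be analysed as Week 17. The SAP window table covers eDiary data only, and SAP Section 1.1 leaves biomarker analyses to a separate plan.
- A reader might infer a loss of precision from comparing smaller samples with 34. The 34 already contains the drop-out allowance, so that is the wrong comparator.
- A reader might infer that the ITT definition presupposes retention, because it includes dosed patients "irrespective of compliance with the study protocol and procedures". That wording sets membership of the population; it neither requires nor assumes later visits.

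The defence is also right that the 7.1.1 pointer is minor: it is conditional, the same section asks for a biopsy, and footnote b names the EoT set. The study is exploratory with no formal testing.

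**Conclusion.** The contradiction stands on the text alone and should be corrected. Its reach is limited. For each patient handled under 6.6, the biopsy and assessments at calendar Week 17, the Week 21 visit and the Week 29 call are lost, as part of 3 to 5 lost contacts. This happens only in people who stopped treatment, and nothing replaces or imputes the missing values.

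The number affected is not stated, and 7.1.1 describes permanent discontinuation as rare. No shortfall in precision against plan is shown. The residual issue is selective missingness, of unknown size, and sites handling the same event differently. The conclusion assumes that footnote b's EoT assessments are carried out at discontinuation. If a site omitted them as well, the loss would be greater, but 6.6 does not tell it to.

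**What to change.** Replace the second sentence of Section 6.6 with: *Patients who discontinue IMP receive no further IMP but remain in follow-up per Section 7.1.1 and SoA footnote b.*

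As a minor alignment, in Section 7.1.1 replace the reference to last-dosing-day procedures with: *the EoT visit (Visit 5) assessments, per SoA footnote b*.

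The cost is one sentence and one phrase at the next amendment. Neither change adds a visit, sample or procedure beyond what footnote b already sets out.
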